	Subject Identification
--	------------------------

Study schema: Shown below.

[figure not shown]
Research Consent Form

General Consent Form Template

Version Date: February 2021

Subject Identification

Study schema

Research Consent Form

General Consent Form Template

Version Date: February 2021

Subject Identification

4. Subject Selection

The proposed study is a double-blind, placebo-controlled, cross-over trial. The study will enroll 10 adult subjects with OUD currently receiving MOUD treatment with sublingual buprenorphine or methadone. Recruitment will occur from the outpatient programs that treat OUD patient at Brigham and Women's Hospital and Brigham and Women's Faulkner Hospital in Boston, MA, and at the Rutland Regional Medical Center in Rutland, Vermont.

Inclusion criteria:

- Age 18 to 65
- English speaking
- Receiving either buprenorphine or methadone for treatment of opioid use disorder for at least 3 consecutive months prior to enrollment
- Agreeable to abstaining from using any cannabis or CBD products for the duration of the trial.

Exclusion criteria:

- Any self-reported use of cannabis or CBD products in the past 30 days
- Current marijuana users
- Baseline depression (PHQ9) or anxiety (GAD7) scores of greater than 10
- Currently pregnant
- Hepatic liver enzymes greater than 3x upper normal limit
- Hypersensitivity to cannabinoids, sesame oil (CBD solution comes in sesame oil emulsion), or artificial strawberry flavoring.
- Currently taking any medications with known significant pharmacokinetic interactions with CBD

Subject recruitment procedures:

- We will use a variety of approaches to recruit for this study. We will use posted flyers at BWH clinical sites where OUD patients are being treated, and advertisements posted on Rally website. We will also utilize the Patient Gateway messages sent directly to active patients by sending an IRB-approved letter for recruitment. Potential participants will be identified by RPDR by searching for any MGB patient being treated with buprenorphine or methadone in their

Research Consent Form

General Consent Form Template

Version Date: February 2021

Subject Identification

medication list and also with a diagnosis of an opioid use disorder. In addition, research staff will approach clinical staff during the staff meetings.

- The RA will be largely responsible for identifying and recruiting potential participants.

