6. STUDY PROCEDURES

Overall approach: A total of 3 study visits are planned (**Table 1**) The first visit is the baseline visit, and the other two are double-blind placebo-controlled medication visits, where either CBD or placebo will be administered. Participants will be randomized using a random-number generator in a 1:1 ratio of CBD to placebo. During the baseline visit, after obtaining informed consent, participants will complete the baseline assessments. The subject will then be scheduled for their study visits 2 and 3 during which they will receive CBD or placebo in random order in double-blind fashion. Visits 2 and 3 will be scheduled at

Research Consent Form**General Consent Form Template****Version Date: February 2021**

Subject Identification

least 1 week apart to function as a washout. Baseline visit will take no longer than an hour, and the subsequent visits will take no more than 2 hours to complete.

Visit 1: Baseline

Participants will provide written informed consent, obtained by the PI or another study physician. The blood and urine samples collected during the Baseline Visit will be used for inclusion/exclusion purposes. Specifically, participants who are currently pregnant (as confirmed by the pregnancy test), or have hepatic liver enzymes greater than three times the upper normal limit (as confirmed by the liver function tests, or LFTs) will be excluded. Subjects will also complete baseline PHQ9, GAD7, BPI, TLFB, COWS, PANAS, and opioid cravings.

Visit 2: CBD or placebo

After arrival to the study site, the participant will receive either the CBD 600mg or placebo, immediately followed by obtaining baseline heart rate, blood pressure, PHQ9, GAD, BPI, TLFB, COWS, opioid cravings, and urine sample for toxicology testing. Heart rate and blood pressure will be monitored every 30 minutes (vital signs: heart rate, blood pressure) following receipt of CBD or placebo. At 60 minutes following the CBD or placebo administration, the participant will then proceed to complete the cue-reactivity test, visual probe task, Iowa gambling task, monetary choice questionnaire (MCQ), and the mirror tracing persistence task (MTPT). Just prior to and after the MTPT task, subjects will provide saliva sample and complete the positive and negative affect scale (PANAS). An additional saliva sample will be collected 20 minutes after the MTPT task.

Visit 3: CBD or placebo

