The same procedures for Visit 2 will be repeated during visit 3, scheduled at least 1 week after visit 2. The order in which CBD or placebo is administered will be randomized.

Cannabidiol:

Research Consent Form

General Consent Form Template

Version Date: February 2021

Subject Identification

Subjects will receive 600mg of oral CBD or matching placebo. Cannabidiol will be provided using Epidiolex™ oral solution 100mg/mL. Drug will be procured by the BWH Investigational Drug Services (IDS) pharmacy and the pharmacy at Rutland Regional Medical Center. The CBD or matching placebo will be placed in oral syringes for the subjects to self-administer at the study site. CBD will be stored at room temperature (68 to 77 F) in its original bottle and in an upright position. Once opened, CBD has a shelf life of 84 days.

Primary Outcome: The primary outcomes is the change in cue-induced cravings (Opioid Craving Scale).

Secondary Outcomes: The secondary outcomes are impulsive decision making (Iowa Gambling Task, Monetary Choice Questionnaire), attentional bias (Visual Probe Task), and physiologic and subjective stress-reactivity.

Assessments:

- Patient Health Questionnaire 9-item (PHQ9): Assessment of depressive symptoms
- Generalized Anxiety Disorder 7-item (GAD7): Assessment of anxiety symptoms
- Brief Pain Inventory (BPI): Pain severity and interference assessment.
- Time-line follow back (TLFB): A method of assessing for recent substance use using a calendar.
- Clinical Opioid Withdrawal Scale (COWS): Assessment of opioid withdrawal.
- Opioid craving scale¹²: A 3-item tool to assess current cravings, cravings when exposed to triggers, and likelihood of using if placed in an environment that the individual previous used opioids.
- Cue-induced craving¹³: Participants will be shown both illicit opioid-related and neutral images on a computer screen for one minute each using a standardized protocol. The order in which the cues will be presented will be randomized and counter balanced. Participants will rate their cravings on a visual analog scale. The cue exposure procedure will end with a standardized debriefing exercise. It is important to note that cue-exposure is a safe paradigm for studying craving in this population when employing debriefing procedures.

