- Monetary Choice Questionnaire (MCQ)¹⁴: This is a 27-item self-report tool used to measure delayed discounting, or the degree to which individuals prefer smaller immediate rewards compared to larger delayed rewards. Participant are asked to choose between a smaller (in dollars) immediate reward and a larger delayed reward.

Study visit number	1	2	3
Informed consent	X		
Pregnancy test	X		
Liver Function Test	X		
Urine toxicology	X	X	X
Heart rate, blood pressure	X	X	X
PHQ9	X	X	X
GAD7	X	X	X
BPI	X	X	X
TLFB	X	X	X
COWS	X	X	X
PANAS	X	X	X
Opioid Cravings	X	X	X
Cue- and stress-reactivity	X	X	
Visual Probe Task	X	X	
Iowa Gambling Task	X	X	
Monetary Choice Questionnaire	X	X	
CBD 600mg or Placebo	X	X	
Adverse effects	X	X	

Table 1: Schedule of assessments

PHQ-9=Patient Health Questionnaire; GAD7=Generalized Anxiety Disorder 7; BPI=Brief Pain Inventory; TLFB=Time-Line Follow Back; COWS=Clinical Opioid Withdrawal Scale; PANAS=Positive and Negative Affect Schedule

Research Consent Form

General Consent Form Template

Version Date: February 2021

Subject Identification

- Iowa Gambling Task (IGT)¹⁵: This is a task to measure decision making, which utilizes four decks of cards (A, B, C, D). Participants are instructed to maximize profits by selecting cards from any deck. Cards from decks A and B earn more profits but lead to even higher occasional losses leading to net long-term losses, while decks C and D yield low profits but only low occasional losses resulting in a net long-term profit.
- Visual Probe Task¹⁶: Opioid-related and neutral images will be used. Each trial will begin with a fixation point lasting 500ms. A pair of images then will appear on the left and right of the screen for either a short (200ms) or long (500ms) stimulus duration to assess automatic orientating and controlled attention processing, respectively. Image pairs will be replaced by a probe in the location of either the opioid-related or neutral image. The probe will remain until the participant responds to identify the probe orientation by pressing the response keys as quickly as possible.

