Cannabidiol medication safety: All subjects in this trial will receive a single dose of 600mg of cannabidiol. Cannabidiol (Epidiolex) is approved by the U.S. Food and Drug Administration (FDA) for the treatment of seizures associated with two rare and severe forms of epilepsy. However, cannabidiol is not approved by the FDA for treatment of opioid use disorder. The PI has conducted a previous pilot trial of CBD 600mg administered to OUD patients for 3 consecutive days in a single-arm open-label design. That protocol was reviewed by the Center for Drug Evaluation and Research at the Food and Drug Administration and determined it met the regulatory criteria for an exemption from the requirement for the Investigational New Drug (IND) submission, and we therefore received the FDA IND exemption letter November 13, 2019. This protocol uses the same medication (Epidiolex), at the same dose (600mg), for the same patient population (OUD on buprenorphine or methadone), and will administer for only one dose instead of three consecutive days. As such, we feel an additional FDA IND is not required to conduct this trial. Although this proposed clinical evaluation is for an "off-label" indication of cannabidiol, it does not involve a route of administration or dosage level or use in a patient population or other factor that significantly increases the risks (or decreases the acceptability of the risks) associated with the use of the Epidiolex (cannabidiol). The proposed dose is within FDA-approved mg/kg maximum daily dose limits. There are now two randomized placebo-controlled studies of administering 400mg or 800mg of cannabidiol to participants with opioid use disorder with no adverse effects. Nonetheless, cannabidiol may cause participants to experience side effects such as: somnolence; decreased appetite; diarrhea; transaminase elevations; fatigue, malaise, and asthenia; rash; insomnia, sleep disorder, and poor quality sleep; infections; and suicidal thoughts or actions. All participants will be told of these potential side effects, and the screening procedures, including liver function tests, are in place to minimize these

Research Consent Form

General Consent Form Template

Version Date: February 2021

Subject Identification

potential risks. The principal investigator will continually assess and monitor adverse effects both during and after cannabidiol administration, as noted in the Schedule of

8. Benefits

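### Pregnancy is tested once, at Visit 1, with no re-test before dosing at Visit 2 or 3 and no maximum interval, so a pregnancy that begins or becomes detectable later can go unnoticed.

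*Combined protocol and SAP*

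**What the plan says.** The exclusion list in Section 4 (Subject Selection) includes "Currently pregnant". The listed criteria admit adults from 18 to 65, with no restriction by sex and no contraception requirement.

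Section 6 (Visit 1: Baseline) says how the exclusion is applied: "The blood and urine samples collected during the Baseline Visit will be used for inclusion/exclusion purposes". It then names "participants who are currently pregnant (as confirmed by the pregnancy test") among those to be excluded. In Table 1 the row "Pregnancy test" carries one mark, against three for urine toxicology and two for study drug.

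Dosing comes later. Under Visit 2, after arrival, "the participant will receive either the CBD 600mg or placebo, immediately followed by obtaining baseline heart rate". The list of assessments that follow the dose ends with a "urine sample for toxicology testing". Visit 3 repeats the Visit 2 procedures and is "scheduled at least 1 week after visit 2". Section 7 (Cannabidiol medication safety) states: "All subjects in this trial will receive a single dose of 600mg of cannabidiol". The order of CBD and placebo is random and double-blind.

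**The concern.** The criterion is applied at entry, but exposure to CBD happens at a later visit, and pregnancy status can change in between. The plan does not limit that gap, and nothing it lists before the dose at Visit 2 or 3 would reveal a pregnancy. The urine collected at those visits cannot do so as written, because it is for toxicology and is listed after dosing.

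Blinding makes both visits matter. Staff cannot know which one carries CBD, so they cannot direct a check to that visit alone.

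What is at stake is participant safety as the plan itself defines it. The documents describe no fetal risk from a single dose, and this point does not rely on one. It rests on the plan's own decision to keep pregnant people out of the study.

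**Working it through.** The plan states no figure to reproduce here. The check sets the relevant provisions side by side and then counts.

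**Sequence of events**

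| Step | Pregnancy test | CBD possible | Timing stated |
|---|---|---|---|
| Visit 1 (baseline) | Yes, once | No | Eligibility is settled before randomization (Section 5) |
| Visit 2 | None stated | Yes | No minimum or maximum from Visit 1 |
| Visit 3 | None stated | Yes | At least 1 week after Visit 2; no maximum |

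**Counts from the documents**

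- Scheduled pregnancy tests: 1. Administrations: 2, of which 1 is CBD. Tests between Visit 1 and either dose: 0.
- Expected number receiving CBD at Visit 3, with n = 10 and 1:1 order: 10 × 0.5 = 5. The other 5 or so are expected to receive it at Visit 2.

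**Interval from test to CBD**

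- CBD at Visit 3: (Visit 1 to Visit 2, no stated limit) + (at least 7 days) = at least 7 days, with no upper bound.
- CBD at Visit 2: neither a lower nor an upper bound is stated.
- The only outer date given is the end of the project period, December 31, 2022. It closes recruitment and is not a window for each participant.

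**How many participants this concerns**

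Let m be the number who can become pregnant. The documents give no sex split, so m could be anything from 0 to 10. The expected number of these receiving CBD at Visit 3 is m × 0.5, which ranges from 0 to 5. Contraception use and actual visit spacing are not given either, so no probability of an exposed pregnancy can be calculated.

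**Size of the remedy**

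- Added tests: 2 × m, so at most 2 × 10 = 20.
- Added time, assuming 5 to 10 minutes for sample and result within the 2-hour visit limit: 5/120 = 4.2% to 10/120 = 8.3%.
- The 60 minutes from dose to tasks is unchanged, because it is counted from the dose.

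**The case against.** The strongest reply is that pregnancy is written as an entry criterion, and the plan does what it says. Eligibility is settled before randomization, and liver function is handled in the same way with one test. Nothing says that either criterion continues to apply up to dosing, so there is no internal contradiction. The trial is small, each person receives CBD once, and Appendix A describes the risk as low and the study as quickly completed. The figure of about 5 counts everyone, whatever their sex or age; the relevant number may be far smaller, possibly zero.

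Much of this stands. The number at risk is unknown, and the small trial and single dose keep the expected number of events low, which limits the weight of the point. It does not close the gap. A remark that the study is short sets no visit window, and the low-risk statement does not address pregnancy. Pregnancy status can change between entry and dosing, and no check before dosing is written down.

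Two uncertainties remain. The study schema, some opening text and the consent pages were not available for this review, so a visit window or pregnancy advice given only there cannot be ruled out. This bears more on the missing maximum interval than on the missing re-test, since Section 6 and Table 1 set out the visit procedures directly. In addition, Section 5 allows a remote baseline visit without saying when blood and urine are then taken. The 7-day minimum assumes that the test is done no later than Visit 2, as the placing of eligibility before randomization implies.

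**Conclusion.** The concern holds. Followed as written, the plan allows a participant who becomes pregnant after Visit 1, or whose pregnancy was too early for the first test to detect, to receive CBD undetected. There is one test, none before either dose, and no upper limit on the interval. For the expected half of participants who receive CBD second, that interval is at least 7 days, if the test precedes Visit 2.

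This should be corrected because it is a safety gap measured against the plan's own criterion and is cheap to narrow. It has no bearing on sample size, power or the analysis.

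**What to change.** For participants who can become pregnant, collect the urine at Visits 2 and 3 before dosing instead of after it, run a urine pregnancy test on that sample, and release product only after a negative result. Add the test to Table 1 at both visits. Testing at both is necessary because the order is blinded, and doing so regardless of order keeps the blind. Management of a positive result stays with the study physicians.

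A negative test before each dose makes a separate maximum interval from Visit 1 largely unnecessary for this purpose.

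The cost is at most 20 test strips, fewer if only some participants can become pregnant, and a short wait before dosing. The visit sequence changes in that dosing must await the sample and result. A urine test can still miss a very early pregnancy, so the change narrows the gap and does not close it completely.

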Adverse reactions to study procedures: The study procedures will end with a standardized relaxation and debriefing exercise. Before participants are discharged from each study session, their well-being will be assessed by the study staff and a standardized safety and adverse events questionnaire will be used to assess any adverse events. If needed, participants will be referred for further clinical evaluation and assistance. It is important to note that cue-exposure and stress-exposure are safe paradigms for studying this patient population when employing debriefing procedures.

Suicidal ideation: Patients with OUD frequently have psychiatric co-morbidities, namely depression. Participants who disclose any suicidal ideation during the study (either through spontaneous expression of suicidal ideation, or self-reported on the PHQ-9) will result in emergent evaluation by a licensed clinician member of the study staff for appropriate assessment and triage. Any disclosures will be handled within existing legal mandates, clinical practice, and social norms. Consistent with standard clinical practice, when possible, disclosures will be discussed with the participant to determine the best management options. This may include notifying the outpatient providers or family members, referring to medical treatment, calling emergency services, or escorting the participant to the Emergency Room at Brigham and Women's Hospital. When required by law, the police department will be notified. The candidate is a board certified psychiatrist and has extensive experience managing acutely distressed patients with mental or substance use disorders.

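### At Visits 2 and 3 the PHQ-9 follows the single oral dose, so ideation first disclosed on that form is evaluated only after CBD may have been swallowed; a pre-dose form with a hold rule is a small, cheap improvement

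*Combined protocol and SAP*

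**What the plan says.** Section 6, Visit 2, sets the order: "the participant will receive either the CBD 600mg or placebo, immediately followed by obtaining baseline heart rate, blood pressure, PHQ9, GAD". The remaining dosing-day baseline measures follow. For Visit 3: "The same procedures for Visit 2 will be repeated during visit 3, scheduled at least 1 week after visit 2". Table 1 lists the PHQ-9 at all three visits but gives no order within a visit, so it does not alter this sequence. Section 6, Cannabidiol, says that the product "will be placed in oral syringes for the subjects to self-administer at the study site".

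Section 7, Suicidal ideation, covers ideation disclosed in either of two ways: voiced spontaneously, or "self-reported on the PHQ-9) will result in emergent evaluation by a licensed clinician member of the study staff". On the management options it adds: "This may include notifying the outpatient providers or family members, referring to medical treatment, calling emergency services". It does not mention withholding the dose and does not place the evaluation before or after dosing.

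Section 7, Cannabidiol medication safety, ends its list of possible side effects with "infections; and suicidal thoughts or actions". The same paragraph gives a reassuring context. Compared with the earlier pilot, this trial "will administer for only one dose instead of three consecutive days", and: "There are now two randomized placebo-controlled studies of administering 400mg or 800mg of cannabidiol to participants with opioid use disorder with no adverse effects".

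**The concern.** The dosing-day PHQ-9 is labelled a baseline measure, and section 7 ties it to an urgent clinical response. Yet it is completed just after the one decision that day which it could inform, namely whether to give the dose. An oral dose cannot be taken back.

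Two things are at stake, both small. First, a clinician could see a positive answer before the dose instead of minutes after it. Second, a positive answer given before dosing is plainly pre-dose. Under the present order it comes after possible exposure to a drug with that listed effect, so its timing is less clear.

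The other baseline measures at these visits also follow the dose. This point covers only the PHQ-9, because it is the form to which section 7 attaches a safety action.

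**Working it through.** The point rests on the order of procedures. The arithmetic only sizes its reach and the cost of the change.

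**1. Is there any scheduled ideation check before the dose on the dosing day?**

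- *Visit 1 PHQ-9 (section 6).* It precedes all dosing. The exclusion in section 4 uses the score (above 10), with no separate criterion for the ideation answer. Section 5 allows the visit to be remote, and the readable text sets no maximum interval to Visit 2.
- *Approval by the treating provider (section 5).* It applies to referred patients and is given before contact. Others come through a website and flyers.
- *Weekly safety meetings (section 10).* These are not same-day checks.
- *Spontaneous disclosure (section 7).* It can occur before the dose and would then be acted on, but it depends on the participant volunteering it.
- *Well-being assessment and adverse events questionnaire before discharge (section 7).* These are same-day, but after the dose.

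None is a scheduled same-day question about ideation before the dose.

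**2. Reach.** Inputs: 10 participants (section 4), two dosing visits each (section 6), one CBD dose each (section 7).

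- Dosing visits: 10 × 2 = 20. With a scheduled PHQ-9 before the dose on that day: 0.
- CBD doses: 10 × 1 = 10. Blinded staff cannot tell which, so a check must apply at all 20 visits.
- Under 1:1 order, 10 × 0.5 = 5 CBD doses are expected at Visit 2, where the latest earlier PHQ-9 is from Visit 1. The other 5 are expected at Visit 3, where it is from Visit 2, at least 7 days before.

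The documents give no rate of positive answers, and none is assumed.

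**3. Time.** Section 6 limits the visit to 2 hours, with 60 minutes from dose to tasks and a saliva sample 20 minutes after the mirror tracing task.

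- Outside the two fixed waits: 120 − 60 − 20 = 40 minutes.
- PHQ-9 at an assumed 2 to 5 minutes: 2/40 = 5% to 5/40 = 12.5%.

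Those 40 minutes are not spare. They must hold arrival, five tasks, the PANAS and saliva collection around the stressor, the debriefing, and the discharge check with its questionnaire. Some of this might fit into the 20-minute wait; the documents do not say. At present the PHQ-9 sits inside the 60-minute wait and adds no visit time. Moved forward, it does.

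**4. Power if a held visit is lost.** Inputs from section 9: mean change 1.5 in absolute value, SD 1.5, r = 0.60, two-sided alpha 0.05, paired t-test.

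- SD of the difference = 1.5 × √(2 × (1 − 0.60)) = 1.342
- Standardised effect = 1.5 / 1.342 = 1.118
- Power from the noncentral t distribution with n − 1 degrees of freedom and noncentrality 1.118 × √n:

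| n | Noncentrality | Power |
|---|---|---|
| 10 | 3.536 | 88.1% (plan states 88%) |
| 9 | 3.354 | 83.5% |
| 8 | 3.162 | 77.4% |

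The plan's figure is reproduced. Reordering alone changes no input and costs no power; only a lost, unreplaced participant does.

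**The case against.** The strongest reply is that nothing is broken. Section 7 requires evaluation and triage, not a dose hold, and both work as written after the dose. A participant with a positive form is evaluated urgently while on site and is checked again before leaving. Exposure is one supervised dose, and the plan reports two randomised studies in this population without adverse effects. The count of 0 in 20 restates the order of procedures and is not an estimate of harm. All of this stands, and it keeps the point minor.

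A reader might infer that all ideation reported on a dosing day is evaluated only after dosing. The documents do not support that: ideation voiced on arrival triggers evaluation when it is voiced. Only ideation first disclosed on the form is affected. A reader might also infer that the order exposes participants with existing ideation to a known added harm. No document links a single dose to worsening of existing ideation.

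Two further objections stand in part. Moving the form alone guarantees nothing; it needs a hold rule, which is a new procedure. And the documents describe the PHQ-9 only as a measure of depressive symptoms, with no recall period, so how closely it reflects ideation at that moment cannot be confirmed from them. Section 7 nevertheless treats an answer on it as grounds for urgent evaluation, and that is enough to want the answer before the syringe.

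**Conclusion.** The point holds as a minor, optional safety improvement. Its reach is all 20 dosing visits, 10 of them with CBD. The size of the benefit is unknown, because the documents give neither a rate of positive answers nor a risk from one dose in someone with ideation. A positive answer is not itself a harm, and the clinician might still give the dose.

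The conclusion assumes that staff follow the written order in section 6, that 10 participants complete both visits, and that the form takes 2 to 5 minutes. The sample size and primary analysis are unaffected unless a participant is lost.

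**What to change.** Change the Visit 2 paragraph of section 6, which carries over to Visit 3, along these lines:

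> On arrival the participant completes the PHQ-9, and study staff read the ideation item before the syringe is handed over. If it is positive, the dose is held until the clinician evaluation described in section 7 is done. The evaluating clinician then decides, without unblinding, whether the dose is given, postponed or cancelled. The interval of 60 minutes from dose to tasks is unchanged.

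**Cost.** One scheduled form moves earlier, and one hold rule is added. Section 7 already requires the licensed clinician. The form leaves the post-dose wait and adds an assumed 2 to 5 minutes to a tight 2-hour visit. A held visit may run past 2 hours, since the evaluation time is not costed, or may be postponed. Postponing Visit 2 or Visit 3 stays within the protocol, because the readable text sets a minimum spacing of one week and no maximum. A participant lost through a hold and not replaced would take power from 88.1% to 83.5%; a second such loss would take it to 77.4%.

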No benefits can be guaranteed from participation in the study. However, all enrolled participants will be receiving an adjunctive agent that is hypothesized to help reduce cue-induced cravings associated with their opioid use disorder, and it is possible that at least some subjects will experience a decrease in the severity of their cravings or stress-reactivity. An extensive screening procedure will ensure that individuals entering the trial will have no contraindications. Trained research personnel will perform all study procedures to minimize risks, discomforts, and adverse effects. Buprenorphine and methadone treatment are FDA-approved treatment for the treatment of OUD, and reduces illicit opioid use and related morbidities associated with OUD. This study will generate valuable information about the effect of combining cannabidiol with stable doses of buprenorphine or methadone for patients with OUD. The results will help inform the direction needed to take in developing effective strategies to improve the care of OUD patients taking medications. If successful, this line of research has the potential to significantly impact clinical practice of treating OUD by providing a viable medication adjunct to existing evidenced-based therapies.

9. Statistical Analysis

For all analyses, descriptive statistics will be used to summarize the data. All comparisons will utilize paired t-tests or non-parametric tests where appropriate. Alpha will be set at 0.05 for all analyses.

Primary outcome:

- Cue-reactivity: Cue-reactivity will be defined as the difference between baseline craving scores and the craving scores in response to opioid-related or neutral cues.

Secondary outcome:

- Subjective cravings: Craving scores will be rated on a 0 to 10 visual analog scale for each of the 3 items.
- Attentional bias: This is calculated as the difference in reaction time (RT) between when the probe replaced the neutral compared with the opioid-related images (i.e. RTneutral – RTopiod).
- Delayed discounting: Based on their responses to the MCQ, the rate of discounting, or k value, is calculated, which range from 0.00016 to 0.25. Higher values indicate greater discounting and impulsivity.

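### The secondary outcome of subjective cravings has no analysis time point, and its only explicitly scheduled rating at the dosing visits is the baseline one taken immediately after dosing

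*Combined protocol and SAP*

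**What the plan says.** Section 9 of the combined protocol and SAP lists, under secondary outcomes, "Subjective cravings: Craving scores will be rated on a 0 to 10 visual analog scale for each of the 3 items". It gives no time point. The same section says that comparisons use paired t-tests or non-parametric tests at alpha 0.05.

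Section 6 describes the instrument as "A 3-item tool to assess current cravings, cravings when exposed to triggers, and likelihood of using" in a setting where the person used opioids before. At Visit 2 the dose comes first, "immediately followed by obtaining baseline heart rate, blood pressure, PHQ9, GAD, BPI, TLFB, COWS, opioid cravings, and urine sample for toxicology testing". Testing follows later: "At 60 minutes following the CBD or placebo administration, the participant will then proceed to complete the cue-reactivity test, visual probe task, Iowa gambling task", then the Monetary Choice Questionnaire and the mirror tracing task. The 3-item scale is not in that list. For the other dosing visit, "The same procedures for Visit 2 will be repeated during visit 3".

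Two further statements in Section 6 bear on whether the scale is used again. The primary outcome is given as "The primary outcomes is the change in cue-induced cravings (Opioid Craving Scale"), and Section 2 names the same instrument. The description of the cue test says only "Participants will rate their cravings on a visual analog scale", without the number of items.

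**The concern.** A treatment outcome should be measured when the treatment can be expected to act. Here the one rating with a stated place in the dosing visit belongs to a set that the plan itself calls baseline, and it precedes the 60-minute test battery. Section 9 also uses baseline craving as the reference for the primary cue-reactivity difference. Followed literally, the plan would use one early score both as the baseline for the primary outcome and as a secondary outcome.

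The risk is a reported lack of effect on subjective craving that reflects the timing of the rating and not the drug. Such a result could be read as evidence against CBD, or as contradicting a positive primary result. If the early rating is the one used, the problem affects all 10 × 2 = 20 dosing visits.

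**Working it through.** **Schedule, set side by side (Section 6)**

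| Measure | Scheduled time at Visits 2 and 3 |
|---|---|
| Opioid cravings | In the baseline set, immediately after dosing |
| Vital signs | In the baseline set, then every 30 minutes |
| PANAS | Before and after the mirror tracing task |
| Saliva | Before, after and 20 minutes after the mirror tracing task |
| Cue test and other tasks | From 60 minutes |

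Where the plan wants a repeat it says so. It states none for the craving scale.

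**Two readings**

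1. The early rating is the only 3-item rating. The outcome is then a score from the plan's own baseline set.
2. The three items are also the cue-test rating, as the primary-outcome label suggests. The later score is then cue-provoked and overlaps the primary outcome.

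Neither reading gives a separate 3-item rating in the test window before cues are shown.

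**The plan's own power figure**

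Inputs from the power paragraph of Section 9: mean change −1.5, SD 1.5, correlation 0.60, n = 10, two-tailed alpha 0.05, paired t-test.

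- SD of the paired difference = 1.5 × √(2 × (1 − 0.60)) = 1.342
- Standardised difference = 1.5 / 1.342 = 1.118
- Noncentrality = 1.118 × √10 = 3.54, with 9 degrees of freedom
- Exact noncentral-t power = 88.1%, which matches the stated 88%

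This figure is for cue-induced craving. The plan gives no power for subjective cravings.

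**Illustration for the early rating (reading 1)**

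Assume that the 3-item scores share these inputs, and that a fraction f of the 1.5-point effect is present at the time of rating. The noncentrality is then f × 3.54.

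| f | Difference in points | Power |
|---|---|---|
| 0 | 0 | 5.0% (equal to alpha) |
| 0.10 | 0.15 | 6.2% |
| 0.25 | 0.375 | 12.5% |
| 0.50 | 0.75 | 35.2% |
| 0.75 | 1.125 | 65.7% |
| 1.00 | 1.5 | 88.1% |

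The documents do not give f. The baseline label and the 60-minute wait suggest that it is small, but that is an inference.

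**The case against.** The strongest reply is that the documents do not rule out a second rating. Sections 2 and 6 name the Opioid Craving Scale for the cue-induced outcome. Section 6 defines that scale as three items, and both the items and the cue-test rating are described as visual analog scales. So the three items may well be what participants rate at the cue test. This stands: a repeat is unclear, not excluded. It does not settle the matter, because Section 6 describes the scale and the cue test as separate assessments, and a rating given to cues is not independent of the primary outcome.

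A second reply is that nothing says the early score is the one to be analysed, since its documented role is baseline. That is also fair, and it is why the low power is stated conditionally.

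Three stronger conclusions are tempting, and the documents do not support them:

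- **The comparison is null by construction.** This needs an onset time for oral CBD, which the plan does not give. The exact clock time of the early rating is not stated either; it is listed after vital signs and several questionnaires.
- **Table 1 shows a single craving rating per visit.** PANAS also has one mark per visit and yet is given before and after the stress task, so one mark proves nothing about repeats.
- **The trial cannot separate background craving from cue reactivity.** Neutral images are shown in the same 60-minute test, and Section 9 refers to craving in response to them, so a rating that bears on this is planned.

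**Conclusion.** The concern holds as a gap in timing and definition. Section 9 names a secondary outcome without a time point, and the only explicitly scheduled 3-item rating at the dosing visits is the baseline one immediately after dosing. Whether the items are rated again at the cue test cannot be settled from the text.

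If the early rating is analysed, the comparison is largely uninformative: power is about 5% to 12.5% when between none and a quarter of the assumed effect is present. That range rests on inputs borrowed from the primary outcome and on an unknown early effect.

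The primary outcome is not made null by this, because its cue response is rated at 60 minutes or later. The weight of the point is moderate: the outcome is secondary, and only Section 9 lists it as such (Sections 2 and 6 do not). It should still be corrected, because the remedy is cheap and gives a better measurement than the schedule as written.

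**What to change.** 1. In the Visit 2 and Visit 3 procedures of Section 6, add the 3-item Opioid Craving Scale at 60 minutes, just before the cue-reactivity test.
2. In Section 9, define subjective cravings as this 60-minute score, compared within person between CBD and placebo.
3. State which instrument, and how many items, the cue test uses, so that the primary-outcome label and the cue-test description agree.
4. State which craving score is the baseline in the primary cue-reactivity difference. This is essential once the scale is given twice before the cues, because there are then two candidates.

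The cost is about one minute per dosing visit and short text changes in Sections 6 and 9. The drawback is one more craving rating shortly before the cues, which is the same under CBD and placebo.
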